4.3. Clinical Experience

Proprietary and Confidential

Page 22 of 127

4.3.1. Clinical Pharmacokinetics of NB-001

After oral administration to healthy adult males (**1999**); Kumagai et al. 1999), NB-001 was rapidly absorbed, with time to maximum plasma concentrations typically observed around 1 hour after administration. Subsequently, plasma NB-001 concentrations declined with a half-life of approximately 4 hours. In this single dose escalation trial, NB-001 exhibited a dose proportional increase in plasma exposure (maximum plasma concentration [C_{max}] and area under the concentration time-curve between zero and infinity [AUC_{0-inf}]) in the dose range 50 mg to 800 mg. At the 200 mg dose level, consumption of food did not have a significant effect on NB-001 exposure. In a multiple dose PK assessment, after administration of NB-001 200 mg 3 times daily (600 mg total daily dose) for 7 days, no significant accumulation was observed. Renal clearance was the major elimination pathway of NB-001, with 80% of the administered drug recovered in the urine within 24 hours after oral administration.

Proprietary and Confidential

Page 23 of 127

Additional details are available in the Investigator's Brochure.

4.3.2. Rationale for Measuring 4β-Hydroxycholesterol in this Study

In *in vitro* and clinical studies, it has been shown that cholesterol is metabolized to 4β -hydroxycholesterol by cytochrome P450 (CYP)3A4 and 4β -hydroxycholesterol concentrations can be used as an endogenous marker for CYP3A4 activity (Bodin et al. 2001; Kanebratt et al. 2008). A comprehensive literature review has concluded that 4β -hydroxycholesterol could in fact be used as a biomarker to detect CYP3A4 induction after at least 2 weeks of treatment with a new molecular entity (Penzak and Rojas-Fernandez 2019). With regards to NB-001, *in vitro* studies with cryopreserved human hepatocytes indicate that NB-001 is not likely to be a clinically relevant inducer of CYP3A4 *in vivo*. Furthermore, archived plasma samples from a previous NB-001 dose escalation study in adolescents were retrospectively analyzed for 4β -hydroxycholesterol concentrations which did not show evidence of CYP3A4 induction indicating NB-001 is not a CYP3A4 inducer *in vivo*. Plasma samples are planned to be collected from subjects enrolled in this study for prospective analysis of 4β -hydroxycholesterol concentrations to confirm previous findings.

5. TRIAL OBJECTIVES AND ENDPOINTS

5.1. **Objectives**

5.1.1. Primary Objective

• To assess the safety and tolerability of NB-001 during 6 weeks of treatment with NB-001 in subjects with 22q11DS

5.1.2. Secondary Objectives

- To assess the efficacy of NB-001 after 6 weeks of treatment with NB-001 using the following endpoint:
 - Clinical Global Impression (CGI)
- To assess the efficacy of NB-001 using a scale specific to the following domain/symptom of greatest impairment for each subject based upon baseline clinical assessment:
 - Anxiety (generalized anxiety disorder [GAD], social phobia [SoP], or separation anxiety disorder [SAD]);
 - Attention and executive deficits (ADHD);
 - Social interaction and repetitive tendencies (i.e., ASD);
- To assess the efficacy of NB-001 using scales specific to the additional symptom domains above

5.1.3. Exploratory Objective

•

5.2. Endpoints

5.2.1. Primary Endpoint

• Type, frequency, severity, and causality of TEAEs, treatment-emergent serious adverse events (TESAEs), clinically significant changes from baseline in: laboratory tests, electrocardiograms (ECGs), vital signs, and physical examination findings during treatment with NB-001

5.2.2. Secondary Endpoints

- Clinical Global Impressions-Improvement (CGI-I)
- Clinical Global Impression-Severity (CGI-S)
- Pediatric Anxiety Rating Scale (PARS)

Proprietary and Confidential

- Attention Deficit Hyperactivity Disorder-Rating Scale-5 (ADHD-RS-5)
- Social Responsiveness Scale, Second Edition (SRSTM-2)

5.2.3. Exploratory Endpoint

•

6. INVESTIGATIONAL PLAN

6.1. Overall Trial Design

[figure not shown]
This is a Phase 2, randomized, placebo-controlled crossover trial to assess the safety and efficacy of NB-001 in children and adolescents with 22q11DS that manifest commonly associated neuropsychiatric conditions. (NOTE: Reference to the 'Investigator' throughout this document refers to the Principal Investigator or, if delegation of responsibilities has been documented, may apply to a sub-Investigator or other clinical trial site personnel.)

The trial is designed to allow all visits to be conducted via telephone and/or video (i.e., telemedicine) or by home health nurse. An in-person visit is required at Screening unless site or government mandates restrict this due to coronavirus disease 2019 (COVID-19). Other in-person visit(s) may occur, if indicated, based on the Investigator's clinical judgement. Subjects will be screened to confirm eligibility and then randomized in a 1:1 ratio to one of two treatment sequences: NB-001(active drug product) followed by placebo (treatment sequence A/P) or placebo followed by NB-001 (treatment sequence P/A). During the Double-Blind Treatment Phase, the subject and/or parent/legal guardian (henceforth, 'parent/guardian') will be contacted at Day 0 to complete baseline symptom scales and will begin dosing with the investigational product (IP; NB-001 or placebo) on the morning of Day 1. Subjects or their parent/guardian will administer the IP BID and will be contacted at Days 0, 1, 14, 28, 42, 49, 50, 63, 77 and 91 to evaluate measures of safety and efficacy, including the completion of symptom scales. In addition, the subject and/or parent/guardian will be contacted at Days 7, 21, 35, 56, 70 and 84 to assess subject safety. Blood samples for PK analysis, 4β-hydroxycholesterol and plasma proline will be collected at the timepoints noted in Table 3. During the Double-Blind Treatment Phase, subjects will receive IP corresponding with the first treatment assignment for 6 weeks (Treatment Period 1), followed by an intervening wash-out period of 1 week, and then will receive their second treatment assignment for the subsequent 6-week period (Treatment Period 2). All symptom scales will be centrally and/or locally administered.

The subject and/or parent/guardian will be contacted for an End of Trial Visit to occur 4 weeks following the last dose of IP to assess safety. If the Investigator perceives a subject is experiencing clinical benefit to treatment and the subject has completed the trial, provisions may be made to allow the subject to continue to receive NB-001. Details will be provided in a separate open-label extension protocol.

A schematic of the trial design is provided in Figure 1 and the Schedule of Assessments is provided in Table 3.

Figure 1: Trial Design

Protocol: NB-001-01 Version: 3.1 / 06JUN2022

| Schedule of Assessments |
|-------------------------|
| Table 3: |

| | Screening Period ^a | | | | | | | ouble- | Double-Blind Treatment Phase | [] reatm | ent Ph | ase | | | | | | End of Trial ^u |
|---|----------------------------------|------------------|----------------|------------|---------------------------|------------|------------|------------|--|-------------------|---------------------------|------------|----------------|------------|------------|------------|---------------------------|------------------------------|
| | | | NOTE | : Grey h | ighlight | s below r | eflect vi. | sits when | NOTE: Grey highlights below reflect visits where a home health nurses is required to support the visit for all subjects. | health m | trses is n | equired t | o suppor | t the visi | it for all | subjects | | |
| Visit/Assessment Day | -28 to -1 | 01 | 1 | Ъ | 14 | 21 | 28 | 35 | 42 ^m | 49 ^{1,0} | 50 ¹ | 56 | 63 | 70 | 77 | 84 | 91/ ET ^t | 119 |
| Visit Window | 4 weeks | | | ±3 days | ±3 days | ±3 days | ±3 days | ±3 days | ±3 days | ±3 days | | ±3 days | ±3 days c | ±3 days | ±3 days | ±3 days | ±3 days | ±3 days |
| Informed Consent/Assent | Х | | | | | | | | | | | | | | | | | |
| Inclusion/Exclusion Criteria | X ^b | X ^b | | | | | | | | | | | | | | | | |
| Demographics | Х | | | | | | | | | | | | | | | | | |
| Medical History | X° | X° | | | | | | | | | | | | | | | | |
| Physical Examination ^s | X | Х | | | | | | | X | | | | | | | | Х | Х |
| Vital Signs ^s | Х | Х | X ^k | | \mathbf{X}^{k} | | | | X | | Xk | | Xk | | | | Х | Х |
| Clinical Laboratory Tests ^{d,s} | Х | Х | | L | · | L | L | ļ | X | |   | | | | |   | Х | Х |
| Serum Pregnancy Test ^{f,s} | Х | | | L | | L | L | ļ | Х | |   | | | | |   | | Х |
| Urine Pregnancy Test ^{f,s} | | Х | | | Х | |   |   | | | Х | | Х | | | | Х | |
| Urine Drug Test ^s | Х | X^k | |   | \mathbf{X}^{k} | L | L | ļ | X ^k | | \mathbf{X}^{k} | | X ^k | | |   | \mathbf{X}^{k} | X^k |
| Sample for Centralized 22q11DS Genotype ^e | Х | | | | | | | | |   |   | | | | | | | |
| Plasma Proline Sample (fasted) ^s | Х | | | | | | | | | | | | | | | | | |
| 12-lead ECG ^s | Х | Х | |   | |  |   | | X | |   | | | | | 1 | Х | Х |
| C-SSRS ⁱ | Х | X^{i} | | | Х | | Х |   | X | Х |   | | Х | | Х |   | Х | Х |
| ADHD-RS-5 ^g | Х | Х | | | Х | | Х | | Х | Х | | | Х | | Х | | Х | Х |
| SRS^{TM} - 2^{g} | Х | Х | | | Х | | Х | | Х | Х | | | Х | | Х | | Х | Х |
| WASI-II IQ Assessment ^{g,h} | Х | | | | | | | | | | | | | | | | | |

Proprietary and Confidential

Page 29 of 127

Protocol: NB-001-01 Version: 3.1 / 06JUN2022

| | Screening Period ^a | | | | | | Г | ouble | -Blind | Double-Blind Treatment Phase | nent P | hase | | | | | | End of Trial ^u |
|--|----------------------------------|----|------|------------|------------|------------|------------|------------|-----------------|--|----------------|------------|---------------------------|------------|------------|------------|------------------------|------------------------------|
| | | | NOTE | : Grey h | ighlight | s below r | eflect vis | sits wher | e a hom. | NOTE: Grey highlights below reflect visits where a home health nurses is required to support the visit for all subjects. | urses is | requirea | to suppo | ort the vi | sit for al | ll subject | s. | |
| Visit/Assessment Day | -28 to -1 | 01 | 1 | ٢ | 14 | 21 | 28 | 35 | 42 ^m | 49 ^{1,0} | 501 | 56 | 63 | 70 | 77 | 84 | 91/ ET ^t | 119 |
| Visit Window | 4 weeks | | | ±3 days | ±3 days | ±3 days | ±3 days | ±3 days | ±3 days | ±3 days | | ±3 days | ±3 days | ±3 days | ±3 days | ±3 days | ±3 days | ±3 days |
| PARS ^{g.j} | х | Х | | | x | | x | | × | Х | | | x | | x | | Х | х |
| CGI-S ^{gj} | Х | Х | | | X | | x | | x | Х | | | x | | x | | Х | Х |
| CGI-Isi | | Х | | | x | | x | | x | Х | | | x | | x | | Х | х |
| Pharmacokinetic Sampling ^s | | | X | | X | | | | | | X ⁿ | | \mathbf{X}^{n} | | | | | |
| Sampling for 4β- hydroxycholesterol (pre- dose) ^s | | | X | | × | | | | | | Х | | X | | | | | |
| Randomization | ьХ | | ļ | ļ | · | L |   | | | | | | | | | | | |
| IP Dispensed ^o | X | | X | | x | | x | | | | Х | | х | | х | | | |
| IP Accountability and Compliance ^s | | | | × | × | × | × | x | x | × | | Х | X | X | X | X | Х | |
| Assess COVID-19/Stressor Impact | | Х | | | | | | | Х | | | | | | | | Х | |
| Concomitant Medications and Therapics ^s | Х | Х | Х | Х | Х | Х | Х | Х | Х | Х | Х | Х | Х | Х | Х | Х | Х | Х |
| Assess Adverse Events ^{p,s} | X° | Xc | X | × | x | x | X | x | x | Х | Х | х | х | х | х | х | Х | Х |
| | | | | | | | | | | | | | | | | | | |

Improvement, CGI-S = Clinical Global Impression-Severity, COVID-19 = coronavirus disease 2019; C-SSRS = Columbia–Suicide Severity Rating Scale; DNA = deoxyribonucleic acid; ECG = electrocardiogram; ET = early termination; IP = investigational product; PARS = Pediatric Anxiety Rating Scale; SRSTM-2 = Social Responsiveness ^a The Screening Period may occur up to 4 weeks prior to dosing (Day 1); eligibility must be determined prior to dosing. Efforts should be made to complete Screening procedures and obtain results within the first 3 weeks of the Screening Period. This will allow time to randomize the subject and ship IP in advance of dosing on Day 1. The Investigator should contact the Medical Monitor if there is a significant delay between completion of all Screening activities and Day 0 and Day 1. An in-person visit is required at Screening unless site or government mandates restrict this due to COVID-19. Scale, Edition 2; WASI-II IQ = Wechsler Abbreviated Scale of Intelligence, Second Edition

Proprietary and Confidential

Page 30 of 127

| Protocol: NB-001-01 Version: 3.1 / 06JUN2022 |
|--|
| ^b Review Inclusion/Exclusion Criteria and confirm eligibility prior to randomizing the subject, prior to dispensing IP, and on Day 0 (prior to first dose on Day 1). ^c Medical history will be documented during Screening and updated on Day 0 to confirm trial eligibility. Any confirmed Diagnostic and Statistical Manual of Mental Disorders, Fifth Edition (DSM-5) diagnoses should be documented as medical history. ^d Clinical laboratory tests include hematology, serum chemistry, urinalysis and Other: eGFR, as described in Table 5. ^e A blood sample will be collected for centralized confirmation of the subject's 22q11DS genotype. If any blood remains from the collected sample, it will be stored and may be used for future research. (Refer to Section 12.1.5.) The subject and/or parent/guardian have the option to decline future research on any remnant blood sample. |
| ⁶ Females of childbearing potential only. ⁸ When possible, to be completed in consecutive order as listed here in Table 3. ^b The WASI-II IQ Assessment should be one of the final clinical assessments completed during Screening and as near as possible to Day 0. ^b After Screening, the C-SSRS will be performed remotely by the local rater via telephone or video (i.e., telemedicine). The C-SSRS should be repeated on Day 0 if more than 21 |
| ^d Performed remotely by central raters via telephone or video (i.e., telemedicine). A rating of the PARS, CGI-S and/or CGI-I by the local rater is optional. When possible local raters may participate in the telephone or video PARS interview and/or asynchronously review the PARS, traters waudio recording to complete their PARS rating. In order to complete the CGI-S and/or CGI-I rating, the local rater must participate in the PARS interview or review the PARS interview and/or cording of the PARS interview. The CGI-I and CGI-S scales will be the last rating scale assessment performed at each visit indicated above. CGI-I assessments at Assessment Days 14, 28, 42 and 49 should use the Assessment Day 0 CGI-S baseline rating as reference for change. CGI-I assessment Days 63, 77, 91 and 119 should use the Assessment Day 49 CGI-S baseline rating as reference for |
| change. (Refer to Section 11.1) ^k Performed only if clinically indicated (i.e., subject exhibits signs or symptoms that require further evaluation), or as deemed necessary by the Investigator. ¹ Day 0 and Day 1 may occur on the same calendar date so long as the procedures required for Day 0 (baseline) are completed prior to subject dosing. Similarly, Day 49 and Day ⁵ 0 may be combined to occur on the same calendar date so long as the procedures required for Day 49 are completed at the end of the wash-out period and prior to dosing. Note |
| that pre-dose samples are required on Day 1 and Day 50. ^m Day 42 will be the last day of dosing for Treatment Period 1. The last assessment of Treatment Period 1 should be completed before the wash-out which, generally, will start on ^m Day 43 and proceed through Day 49. The subject will start Treatment Period 2 and resume dosing on Day 50. ^m Days 1 and 14 pharmacokinetic (PK) samples and Days 50 and 63 PK samples will be collected pre-dose (morning), then at 1 and 4 hours post-dose. |
| ^o Dosing will be paused from Days 43-49 (generally), during the wash-out period. No capsules will be taken during this time. ^p Adverse Event (AE) recording will occur from the time of signing the informed consent form and, if applicable, the subject assent form, and through the End of Trial Visit. Home health nurses may supplement the reporting of AEs and Concomitant Medications during home visits; however the Investigator's assessment will supersede that of the home health nurse. Only the Investigator will assign AE Relationship to IP. AEs will be followed until resolution or until deemed stable by the Investigator. |
| ^q Randomization will occur after all Screening procedures are complete and the subject is determined to be eligible for the study. ^r Once the subject is randomized, IP will be sent to the subject's home with instructions to begin dosing on the morning of Day 1 (with guidance from the home health nurse who will collect pre-dose samples on Days 1, 14, 50 and 63, as noted above). Additional IP shipments with supply for approximately 2 weeks of dosing will be sent to the subject or parent/guardian and subjects will be instructed to begin dosing from new supply on Days 15, 29, 50, 64 and 78. |
| ⁸ Procedures and assessments will be performed, laboratory samples collected, AEs and concomitant medications recorded, and IP accountability and dispensation recorded by home health nurses and/or the Investigator. ¹ The end of treatment assessments will be performed at the Day 91 Visit, or if the subject withdraws from the study prior to Day 91 (i.e., early termination), as soon as possible |
| ^{a there the last dose of IP.} ^{a The End of Trial Visit will be performed 4 weeks after the last dose of IP to assess safety. If the Investigator perceives a clinical benefit to any subject who completes the trial, provisions may be made to allow the subject to continue to receive NB-001 and the End of Trial Visit/Assessment Day 119 will not be required. Details will be provided in a separate open label extension protocol.} |
| · I ne physical exam at screening will include a measurement of neight. |
| |

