anxiety (most common), mood disorder, depression, ASD, and bipolar symptoms, and this may account for at least 50% of the general ADHD population. In patients with 22q11DS (who often have comorbid cardiovascular abnormalities in addition to the described neuropsychiatric symptoms), stimulant drugs may not be safe, effective, and/or appropriate. To date, there is no approved medication for the combined/comorbid neuropsychiatric symptoms of 22q11DS (which may include symptoms of ADHD).

Clinical experience in syndromic/comorbid ADHD patients provides further evidence that NB-001 may have positive effects in 22q11DS. In a 5-week, open-label, single-blind, placebocontrolled study of 30 adolescents, ages 12–17 years with ADHD (Study NFC1-2014 [GREAT]), NB-001 improved Clinical Global Impression-Improvement (CGI-I) and Clinical Global Impression-Severity (CGI-S) scores (Elia et al. 2018). Of note, patients were selected for presence of mutations in mGluR network genes, the same major pathway hypothesized to be implicated in 22q11DS.

Proprietary and Confidential

Page 21 of 127

Therefore, the current evidence provides strong rationale for development of NB-001 to treat the psychiatric symptoms of 22q11DS.

Given the totality of data observed to date, including human clinical data and the high unmet medical need for treatments addressing the psychiatric symptoms of 22q11DS, the continued development of NB-001 in 22q11DS seems warranted.

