12.1.2. Vital Signs

Vital signs will include blood pressure (systolic and diastolic), heart rate, respiratory rate, and temperature and will be performed after the subject has been at rest in the seated position for at least 5 minutes. Vital signs will be assessed at the Screening Visit and as clinically indicated per Table 3.

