12.1.4. Electrocardiograms

A 12-lead ECG in triplicate will be obtained at the at the Screening Visit, Day 0, Day 42, Day 91/ET Visit, and End of Trial Visit, with the subject in a supine position following at least a 5-minute rest. The Investigator will review and report the results of each ECG; the reviews on Days 42 and 91 will include a comparison of each ECG to the baseline (i.e., Day 0) ECG. Any clinically significant abnormality should be reported as an AE, as appropriate.

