14. DETERMINATION OF PLASMA NB-001 AND 4B-HYDROXYCHOLESTEROL CONCENTRATIONS

14.1. NB-001 Concentrations in Plasma

Blood samples for determination of NB-001 plasma concentrations will be collected at the time points noted in Table 3. On PK assessment days, the morning dose of NB-001 should be administered during the visit with the home health nurse.

NB-001 plasma concentrations will be compared between subjects, based upon dosing conditions, within this trial (i.e., subjects taking intact NB-001 capsules versus subjects taking NB-001 sprinkled on applesauce) and to historical data. Only PK samples collected during active NB-001 treatment for each subject will be analyzed after all subjects have completed the trial.

NB-001 concentration and other relevant data from this trial may be pooled with data from other studies for nonlinear mixed effects modelling and reported separately.

| Collection of Samples for Plasma Concentrations on Days 1, 14, 50, 63 | | Example Schedule |
|--|--|------------------|
| Pre-dose | Collect PK and 4B-hydroxycholesterol samples | 9:45 am |
| Administer Morning Dose | | 10:00 am |
| 1-hour Post-dose | Collect PK sample | 11:00 am |
| 4 hours Post-dose | Collect PK sample | 2:00pm |
| Administer Evening Dose | | 6:00 pm |

PK = pharmacokinetic(s)

14.2. 4B-Hydroxycholesterol Concentrations in Plasma

Blood samples for the determination of concentrations of 4β -hydroxycholesterol, an endogenous biomarker for CYP3A4 induction, will be collected pre-dose at the visits noted in Table 3. Changes, if any, in 4β -hydroxycholesterol concentrations 2 weeks after the start of IP in subjects assigned to active and placebo arms will be used in the assessment of CYP3A4 induction potential of NB-001.

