4.5.5 Vital Signs, Physical Findings, and Other Observations Related to Safety

4.5.5.1 Vital Signs

Vital sign parameter measurements will be summarized by treatment group. Descriptive statistics will be presented for results and change from baseline at each visit where parameters were scheduled to be collected.

4.5.5.2 12-Lead Electrocardiogram

Select twelve-Lead ECG interval parameters to include heart rate, PR interval, QRS duration, and corrected QT (QTc) interval will be summarized by treatment group. Summaries of ECGs performed in triplicate will be based on the mean of the triplicate measurements at each time point. For visits where the interpretation is provided in triplicate, the worst interpretation will be used for analysis. Descriptive statistics will be presented for observed values and changes from baseline at each visit where parameters were scheduled to be collected.

Twelve-lead ECGs will be classified by the investigator as "normal," "abnormal, not clinically significant," or "abnormal, clinically significant." Three-by-three contingency tables will be presented to summarize the shift from the baseline category to the worst post-baseline value. Summary results will include the count and percentage of subjects within each shift category and treatment group.

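### No vital-sign or ECG reading is required at a known time after dosing, so asymptomatic changes near peak exposure are poorly captured, and the Period 2 vital-sign baseline usually falls on treatment

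*Protocol*

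**What the plan says.** The primary endpoint (Protocol 5.2.1) includes "clinically significant changes from baseline in: laboratory tests, electrocardiograms (ECGs), vital signs, and physical examination findings during treatment with NB-001".

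**Vital signs.** Table 3 (Protocol 6.1) marks them without condition at Screening, Day 0, Day 42, Day 91/ET and Day 119. On Days 1, 14, 50 and 63 the mark carries footnote k: "Performed only if clinically indicated (i.e., subject exhibits signs or symptoms that require further evaluation), or as deemed necessary by the Investigator". Protocol 12.1.2 is worded differently: "Vital signs will be assessed at the Screening Visit and as clinically indicated per Table 3".

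**ECG.** Triplicate ECGs are "obtained at the at the Screening Visit, Day 0, Day 42, Day 91/ET Visit, and End of Trial Visit" (Protocol 12.1.4). None is scheduled on Days 1, 14, 50 or 63. Sections 12.1.2 and 12.1.4 and the matching SAP sections (3.4.2.3, 3.4.2.5) set rest and posture but no time since dose.

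**Dose-timed visits.** Days 1, 14, 50 and 63 have PK samples before the morning dose and 1 and 4 hours after it (Table 3, footnote n). Protocol 14.1 adds: "On PK assessment days, the morning dose of NB-001 should be administered during the visit with the home health nurse".

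**Pharmacokinetics.** Protocol 4.3.1 reports, in healthy adult males, "time to maximum plasma concentrations typically observed around 1 hour after administration" and a half-life of about 4 hours.

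**Analysis.** SAP 4.5.5.1: "Descriptive statistics will be presented for results and change from baseline at each visit where parameters were scheduled to be collected". SAP 4.5 takes as baseline the last measurement before the first dose of each period (Day 1 or Day 50).

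**The concern.** The one visit per treatment at which vital signs and ECG must be taken can fall anywhere in the dosing interval. At the visits where time since dose is known, measurement is conditional. A condition based on signs or symptoms cannot find a change in heart rate or blood pressure that the child does not feel. The stakes are the trial's primary question, in patients "who often have comorbid cardiovascular abnormalities" (Protocol 4.2), with no data monitoring committee planned.

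Two analysis problems follow. A by-visit summary of the footnote-k days would describe whoever was selected for measurement. And because no vital signs are scheduled at Day 49 and those at Day 50 are conditional, the last value before the Period 2 dose will usually be the one from Day 42, taken on the first treatment.

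**Working it through.** The plan states no figure to reproduce here. The check counts the scheduled readings, then sizes exposure at plausible reading times, then traces the baseline.

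**1. Required on-treatment assessments per treatment (Table 3)**
- Vital signs, unconditional: 1 (Day 42 or Day 91/ET).
- ECG, unconditional: 1 (triplicate, same visit).
- Either one at a specified time after dose: 0.

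**2. Exposure relative to peak**

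Inputs: peak at 1 h and half-life 4 h (Protocol 4.3.1). Level relative to the peak at t hours = 2^(−(t−1)/4).

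| Time since dose | Exponent | Share of peak |
|---|---|---|
| 1 h | 0 | 100% |
| 4 h | −0.75 | 59% |
| 8 h | −1.75 | 30% |
| 11.75 h (just before the next dose, 12-hourly dosing assumed) | −2.6875 | 16% |
| 15.75 h (18:00 dose to 9:45 sample, the example in Protocol 14.1) | −3.6875 | 8% |

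A one-compartment curve with absorption set so that the peak falls at 1 h (ka = 3.04/h) gives 63% at 4 h and 32% at 8 h, so the choice of curve matters little.

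**3. How often an untimed visit falls near peak**

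Assume a visit at a random time between 09:00 and 17:00, and doses at either 10:00/18:00 (the protocol's example) or 08:00/20:00 (assumed).
- At or above 80% of daily peak: about 12% and 20% of visits.
- At or above 50%: about 51% and 54%.

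With about 34 subjects, each with one end-of-period visit on NB-001, the expected number read at or above 80% of peak is 34 × 0.12 ≈ 4 to 34 × 0.20 ≈ 7. If visit times are independent, the chance that none is that close is 0.88^34 ≈ 1.3%, or 0.80^34 ≈ 0.05%.

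**4. Period 2 vital-sign baseline**

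Suppose NB-001 shifts a vital sign by d at the end-of-period visit, the effect washes out, and there is no placebo effect. Let baseline fall back to Day 42.
- A/P: NB-001 change = d − 0 = d; placebo change = 0 − d = −d.
- P/A: placebo change = 0 − 0 = 0; NB-001 change = d − 0 = d.
- With equal sequences: mean NB-001 change = d; mean placebo change = (−d + 0)/2 = −d/2; difference = 1.5d instead of d.

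A pre-dose Day 50 reading repairs this: the one-week wash-out is 7 × 24 / 4 = 42 half-lives.

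**5. Internal consistency**

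Section 12.1.2 names Screening and otherwise clinical indication. Table 3 has unconditional marks at Days 0, 42, 91 and 119. The two do not agree.

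**The case against.** The best defence is that the gap is narrower than it looks. Adverse events are assessed at every visit, so a symptomatic effect near peak can be caught. ECGs are in triplicate, and nothing times the placebo visits differently from the active ones. Exclusion 5 removes clinically significant unstable or uncontrolled cardiovascular disease, and the remark on cardiovascular abnormalities is made to explain why stimulants may be unsuitable. Earlier clinical data and the Investigator's Brochure, not visible here, might justify light monitoring. All of this stands. It leaves asymptomatic, transient change as the gap.

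Four stronger readings are tempting and are not supported:
- *A peak effect would go unseen in every subject.* Step 3 shows that some Day 42 and Day 91 visits would very probably fall near peak by chance. Detection is weakened, not absent.
- *Only symptomatic subjects would be measured on the conditional days.* Footnote k also allows Investigator discretion. The subset is selected, but not purely by symptoms. Nor is it clear that SAP 4.5.5.1 counts a conditional mark as scheduled, so those summaries may not be produced.
- *An effect read before the dose would be one sixth of its peak size.* That needs 12-hourly dosing, adult PK and an effect proportional to plasma level. The documents establish none of these for this population.
- *The baseline problem corrupts the change on NB-001.* It does not: that change starts from Day 0 in A/P and normally from Day 42 on placebo in P/A, both free of NB-001. The affected quantity is the placebo change in A/P, and through it the comparison with placebo. The Investigator's ECG review on Days 42 and 91 uses Day 0 as reference.

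**Conclusion.** The point holds as a weakness in measurement. Followed as written, the plan obliges no one to take a vital sign or ECG at a known time after dosing, although both belong to the primary endpoint. A reading at 8 hours would reflect about 30% of peak exposure, and one before the morning dose about 8% to 16%. These figures rest on PK from healthy adult males and, for the 16%, on assumed 12-hourly dosing. They describe exposure, not effect, and nothing in the documents shows that NB-001 has a cardiovascular effect.

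The baseline consequence is separate and does not depend on the PK curve: unless someone happens to measure vital signs between Day 42 and the Day 50 dose, the A/P placebo change starts from an on-NB-001 value. The 1.5d result illustrates the direction and possible size under full wash-out and equal sequences.

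**What to change.** - **Table 3:** remove footnote k from vital signs on Days 1, 14, 50 and 63. Record them in all subjects pre-dose and at the 1-hour PK time point, after the 5-minute seated rest and before the blood draw.
- **Days 42 and 91:** record on the CRF the time of the last dose and of the ECG and vital signs. Where the subject is still dosing, aim for about 1 hour after the morning dose. Early-termination visits are exempt from the timing but record time since last dose.
- **SAP 4.5:** use the pre-dose Day 50 value as the Period 2 vital-sign baseline.
- **Protocol 12.1.2:** reconcile its text with the unconditional marks in Table 3 at Days 0, 42, 91 and 119.

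Visits with required on-treatment vital signs rise from 1 to 3 per treatment, and required readings at the 1-hour point from 0 to 2. Dosing is unchanged.

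The cost is a protocol amendment, a few minutes at nurse visits that already take place, and less freedom in the clock time of Days 42 and 91. The change does not add an off-drug Period 2 ECG baseline, so by-visit ECG change in Period 2 keeps the same limitation.
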